4.4.2.2. Analysis of Adverse Events

Incidence rates of adverse events will be calculated for the BDQ and non-BDQ treated cohorts. Additional descriptive analyses will include incidence rates of adverse events of interest for BDQ treated patients and non-BDQ treated patients calculated by dividing the total number of each adverse event by the total person-exposure time and expressed as the number of events per person-year, and 95% confidence intervals.

Relative risk rates and 95% confidence intervals will be calculated and appropriate stratified analyses will be conducted for each adverse event, including death. Poisson regression models will be used to adjust for potential confounders based on baseline clinical characteristics and patient demographics. Adjustments for imbalances between the treatment groups will be applied using accepted methods based on sample size availability and the observed overlap of key patient characteristics. If the sample size is adequate, propensity score methods may be used to adjust for imbalances between the 2 treatment groups before receiving the BDQ treatment or other MDR-TB therapy. Adjustment methods will be determined *a priori* to any comparative analysis with respect to safety outcomes.

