Data will be collected in an observational manner such that the management of the patient is determined by the patient and the caregiver and not influenced by the registry protocol. The registry will describe care as it is provided.

Relevant Institutional Review Board (IRB)/Ethics Committee (EC) and Health Authority (HA) approvals will be secured prior to initiating the study.

A separate statistical analysis plan and data collection form to meet the registry objectives will be submitted for review.

Analyses of MDR-TB drug susceptibility will use the total number of MDR-TB patients included in the registry. Proportions will describe the number of patients whose post-enrollment isolates exhibit at least 4-fold increase in BDQ MIC in comparison to baseline MIC, provided that the post-baseline MIC is >0.25 mg/mL based on phenotypic methods on solid or liquid media. Additional proportions will describe the number of patients with pre-XDR and XDR-TB.

ABBREVIATIONS

AIDS	Acquired immunodeficiency syndrome
ARV	Antiretroviral
BDQ	Bedaquiline
BMI	body mass index
CDC	Centers for Disease Control and Prevention
CI	Confidence Interval
CRF	Case Report Form
DOT	Directly Observed Therapy
DOTS	Directly Observed Therapy Short-course
DS	Drug Susceptible
EC	Ethics Committee
ECDC	European Centre for Disease Prevention and Control
EEA	European Economic Area
EU	European Union
FDA	United States Food and Drug Administration
GMS	Global Medical Safety
GPP	Good Pharmacoepidemiology Practices
HA	Health Authority
HIV-1	human immunodeficiency virus type 1
IRB	Institutional Review Board
MIC	Minimum inhibitory concentration
MDR-TB	Multi Drug Resistant Tuberculosis
NTM	Nontuberculosis mycobacterium
RMP	Risk Management Plan
SD	standard deviation
SPP	Specialty Pharmacy
SSCT	standard short-course therapy
STROBE	The Strengthening the Reporting of Observational Studies in Epidemiology
TB	Tuberculosis
U.S.	United States
WHO	World Health Organization
XDR-TB	Extensively drug-resistant TB

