1.1.4. Main Treatment Options

The WHO-recommended treatment strategy for DS-TB is directly observed treatment short-course (DOTS). DOTS combines 5 elements: political commitment; microscopy services; drug supplies; surveillance and monitoring systems; and use of highly efficacious regimens with direct observation of treatment. The standard WHO chemotherapy treatment regimen for DS-TB consists of a 2-month intensive phase during which 4 drugs are administered once or twice per week (isoniazid, rifampicin, pyrazinamide, and ethambutol), with a continuation phase of 4 months during which 2 drugs are administered (usually isoniazid and rifampicin) to which the mycobacterium has been demonstrated to be sensitive for 4 months (Chan 2002⁶, Douglas 1999⁸). Streptomycin is also used as a first line drug to treat DS-TB, usually for retreatment of newly diagnosed cases that failed to complete the initial treatment course or are responding poorly to their first course of TB treatment.

MDR-TB is considered curable but cannot be adequately treated with the standard short-course therapy (SSCT) (Chan 2002⁶, Douglas 1999⁸). MDR-TB therapy often requires extensive chemotherapy (up to 2 years of treatment) with a combination of less efficacious second line drugs, requires extensive supervision and treatment costs are extremely expensive. Most authorities recommend a regimen consisting of either 3 or 4 oral anti-TB drugs in combination with 1 injectable drug (Frieden 1999¹²).

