4.2.1. Exposure Definition and Measures

Exposure to MDR-TB regimens will be determined by documentation by the healthcare provider. The initiation date of MDR-TB treatment for each patient will be the drug initiation date as reported by the healthcare provider. The discontinuation date for each drug exposure will be defined as the date the drug was stopped as reported by the healthcare provider. Duration of exposure will be based on initiation and discontinuation dates for each drug. Switches from one drug to another will be captured and time on drug will be defined by the exposure periods.

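### The Poisson comparison in section 4.4.2.2 has no term for time since treatment start, so unequal follow-up between cohorts can move the rate ratio away from 1 with no BDQ effect

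*Protocol*

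**What the plan says.** Estimating the relative risk of adverse events and death, BDQ against no BDQ, is a primary objective (Protocol section 1.3.1). Section 4.4.2.2 handles it in two steps.

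- **Rates.** Under additional descriptive analyses, rates for adverse events of interest are "calculated by dividing the total number of each adverse event by the total person-exposure time", per person-year.
- **Comparison.** Relative risks with 95% intervals follow, and "appropriate stratified analyses will be conducted for each adverse event, including death". On the model: "Poisson regression models will be used to adjust for potential confounders based on baseline clinical characteristics and patient demographics". Propensity scores may be used for imbalances present before treatment. Adjustment methods are to be settled before any comparative safety analysis.

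On time at risk, several places matter:

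- Section 4.2.1 records start and stop dates for each drug: "Switches from one drug to another will be captured and time on drug will be defined by the exposure periods".
- Section 4.2.2.1 defines the treatment-emergent window from BDQ doses only, ending 30 days after the last one. It gives no counterpart for patients not on BDQ.
- Section 2.1 runs follow-up to 24 months after the last BDQ dose, with similar follow-up for the others.
- Section 4.2.4 runs it to 24 months after MDR-TB therapy stops, for every patient.
- Section 1.1.4 puts MDR-TB therapy at up to 2 years.

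The Synopsis adds: "A separate statistical analysis plan and data collection form to meet the registry objectives will be submitted for review". That plan is not at hand.

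**The concern.** A Poisson model with a person-time offset and only baseline covariates compares average rates over whatever time each cohort contributes. If the hazard is higher early in treatment, the cohort observed for less time has a larger share of high-hazard time and so a higher average rate. Baseline covariates cannot remove this. Nor can propensity scores, which balance only characteristics present before treatment.

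The protocol gives reason to expect unequal time. Exposure is recorded drug by drug, one adverse-event window is tied to BDQ alone, and the 24-month follow-up is counted from two different events. Entry differs too: section 2.1 enrols comparators at MDR-TB diagnosis and BDQ patients when BDQ is chosen, which may be after other therapy has begun.

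At stake is a spurious safety signal, or a masked one, in a primary comparison. The yardstick is the relative risk of 2 used for power in section 4.1.

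**Working it through.** **The plan's own figure.** Section 4.1 gives power 0.954 for a relative risk of 2, with 1000 per group and 3% event frequency. A one-sided pooled two-proportion calculation at 0.05 (3% v 6%) gives 0.945, which is close; the two-sided value is 0.900. The figure serves here only to show that 2 is the effect size of interest.

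**Inputs.** From the documents: a regimen of up to 24 months (1.1.4), 24 months of follow-up after treatment (2.1, 4.2.4), and baseline-only adjustment (4.4.2.2). Assumed: BDQ exposure of 6 to 12 months, a hazard in the first 6 months k times the later hazard, k from 2 to 5, and no BDQ effect.

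**Formula, all events.** For d months at risk (d at least 6), the average rate in units of the later hazard is (6k + d − 6)/d. The apparent ratio is this value for the BDQ cohort over the value for the comparator.

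Example with k = 3:
- 6 months: 18/6 = 3.0
- 24 months: (18 + 18)/24 = 1.5
- Ratio: 3.0/1.5 = 2.00

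| BDQ v comparator, months | k = 2 | k = 3 | k = 5 |
|---|---|---|---|
| 6 v 24 | 1.60 | 2.00 | 2.50 |
| 12 v 24 | 1.20 | 1.33 | 1.50 |
| 18 v 24 | 1.07 | 1.11 | 1.17 |
| 30 v 48 | 1.07 | 1.12 | 1.20 |
| 42 v 48 | 1.02 | 1.03 | 1.05 |
| 24 v 18 | 0.94 | 0.90 | 0.86 |
| equal lengths | 1.00 | 1.00 | 1.00 |

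The first two rows set BDQ drug time against a whole regimen. The 18 v 24 and 24 v 18 rows compare whole regimens. The 30 v 48 row adds 24 months to a 6-month BDQ course and to a 24-month regimen; the 42 v 48 row adds 24 months to regimens of 18 and 24 months. With k = 1 every ratio is 1.00.

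**First events.** For death, or for a first occurrence, patients leave the risk set after the event. With a later hazard of 0.01 per month (assumed), 6 v 24 months gives 1.56, 1.91 and 2.28 for k = 2, 3 and 5. 12 v 24 months gives 1.19, 1.31 and 1.45. Adding a month to BDQ time for the 30-day tail (7 v 24, k = 3) gives 1.74.

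**Fitted models.** 300 simulated data sets per case, 1000 per group, true ratio 1, one baseline covariate, log person-time offset, test at 0.05, k = 3:

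| Months | Ratio, no time term | Rejections |
|---|---|---|
| 6 v 24 | 1.90 | 100% |
| 12 v 24 | 1.31 | 84% |
| 30 v 48 | 1.11 | 32% |
| 42 v 48 | 1.02 | 8% |
| 24 v 24 | 1.00 | 6% |

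Adding a two-level time band (0–6 months, later) returned ratios of 0.99 to 1.00 and rejection of 3% to 7% in all eight cases run (these five plus 7 v 24 at k = 3, and 6 v 24 at k = 1 and 2).

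The rejection rates reflect a common event: at k = 3 the 24-month risk is 1 − exp(−(6 × 0.03 + 18 × 0.01)) = 1 − exp(−0.36) = 30%. For rarer events the ratios move towards the all-events table and false rejections become fewer.

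**The case against.** The strongest answer is that the protocol does not commit to what the calculation assumes.

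- **The model.** A reader might infer that section 4.4.2.2 fixes a single constant rate per cohort. It does not say so. The sentence on Poisson regression lists what is adjusted for, not the time scale. The denominator of total person-exposure time belongs to a sentence on descriptive rates. Stratified analyses are planned with unnamed strata, methods are to be set before the comparison, and a separate analysis plan could supply time bands. All this stands. Even so, the section does name a model and an adjustment set, and time since start is not in it.
- **The 6 v 24 month contrast.** A reader might also infer that BDQ patients are counted on one drug and comparators on a whole regimen. Section 4.2.1 records dates for every drug in every patient and does not say this. Sections 4.2.2 and 4.2.4 point towards whole-course windows in both cohorts. Section 4.4.2.2 does not invoke the BDQ-only window of 4.2.2.1. This stands, and it removes most of the size.
- **The early hazard.** No section gives event timing, so a falling hazard is an assumption. The split into intensive and continuation phases in 4.2.2 makes a flat rate doubtful but does not give a value of k.

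**Conclusion.** The mechanism is sound: followed as written, the stated adjustment leaves the rate ratio open to an artefact whenever a shared hazard changes over time and the cohorts contribute different lengths of time. Its size turns on a risk window that the protocol does not settle.

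- BDQ drug time of 6 to 12 months against a 24-month regimen: about 1.2 to 2.5 for k from 2 to 5, or about 1.56 to 2.28 for first events at 6 v 24 months.
- Whole regimens or whole follow-up in both cohorts: about 1.02 to 1.2.
- BDQ time longer: below 1 (0.86 to 0.94 for 24 v 18 months).

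The course lengths and k are assumptions. The documents do not support saying that the analysis will produce a spurious ratio near 2. They support saying that it could under one reading of exposure time, and that nothing in the stated adjustment prevents it. The correction is worth making for its low cost, but the plan does not fail without it.

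**What to change.** In section 4.4.2.2:

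1. State one time origin for both cohorts, for example the start of the MDR-TB regimen, with late entry at BDQ start or enrolment. The origin must be named because BDQ patients may join after other therapy began (sections 2.1 and 3.1.1). Their time could then miss the early period, which would push the ratio the other way.
2. Split person-time into bands from that origin (for example 0–6, 6–12, 12–24 and over 24 months) and enter the band as a factor in the Poisson model.
3. Estimate rate ratios only over bands in which both cohorts contribute time.
4. Apply the same risk window to both cohorts, and reconcile the follow-up statements in 2.1 and 4.2.4 and the BDQ-only window in 4.2.2.1.

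The cost is wording and a little programming, since section 4.2.1 already collects the treatment dates. Intervals will be slightly wider, and there is no comparison in bands where one cohort has no time.

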4.5. Evaluation of Appropriateness of Comparison Study

The evaluation of appropriateness of a comparison of BDQ-exposed patients with non-BDQ-treated MDR-TB patients will be based on the consistency of the clinical

experience of the 2 cohorts. This assessment will be conducted based on distribution of propensity scores for receipt of BDQ or other treatment regimens.

The evaluation of clinical experience will assess the patients' clinical and demographic characteristics in relation to receipt of BDQ and other MDR-TB regimens. Information will be captured on the patients' clinical and demographic characteristics that could be predictive of treatment appropriateness. This information will be incorporated into multivariate model to identify a group of patients with similar characteristics to the BDQ cohort but treated with other MDR-TB treatments. All patients will be assigned a propensity score ranging from 0 to 1 that represents the fitted probability of receiving BDQ. The scores from non-BDQ-treated patients will be plotted against those for BDQ-treated patients. Overlap in the cohorts based on sample size estimates of approximately 750 patients per treatment group in the propensity space must exist for a comparison of safety events between the two groups. An epidemiologist trained in propensity score estimation and matching methodology will make this assessment on the epidemiological validity of a comparison between the 2 treatment cohorts.

4.6. Data Quality Assurance and Validation Procedures

The registry will be managed by INC Research and will utilize the INC Research Coordinating Center (RCC). INC Research will develop the case report form (CRF) with input from Janssen as well as from INC Research's data management team, biostatistician, epidemiologist, and Project Manager as relevant. Concurrent with the development of the CRF, INC Research will draft CRF completion guidelines for review by the INC Research registry team and Janssen and CRF Completion Guidelines.

INC Research's RCC is staffed with Central Monitoring Associates with varied backgrounds ranging from patient care experience in nursing, to clinically oriented research as study coordinators, call center nurses, or safety specialists, to backgrounds in data management, research project administration, or regulatory document administration. All Central Monitoring Associates undergo extensive training regarding 21 CFR Part 50, 54, 56, 312, 314, the principles of International Conference on Harmonisation (ICH) Guidelines for Good Clinical Practice (GCP) and INC Research standard operating procedures (SOPs).

Staff of the RCC at INC Research are experienced in working directly with both patients and HCPs via telephone and email. Dedicated Central Monitoring Associates will be designated for this registry; however, all Central Monitoring Associates in the RCC are cross-trained on all projects to provide maximum coverage.

A National Coordinator from INC Research will review CRFs for accuracy, identifying missing data and resolving any inconsistencies and transfer key coded data to the RCC within 24 hours of data receipt. Additionally, the National Coordinator will maintain CRFs as well as participant enrollment records and ongoing assessments.

INC Research will use Oracle Clinical RDC Onsite electronic CRFs (eCRFs) to process the data for the registry.

To enable the team to collect data while on the phone with HCPs, paper copies of the CRF, suitable for hand-written completion will also be available to reporters who prefer to complete a paper form, via access from the registry website. Paper forms can be sent to the registry via mail or electronically. Once received by the registry, the data from these forms will be entered into the system by the central monitoring team or the reporters who will have direct access to the data entry system.

Occasionally, HCPs provide patient medical records in lieu of completed CRFs. The registry will review the medical records and transcribe information onto the appropriate CRFs.

Simple on-line checks will be displayed for the Central Monitoring Associates at point of entry, reducing the need for queries. The data management team will perform additional data review of the more complex checks and raise queries with the central monitoring team as required in the EDC system.

Quality measures included in the registry include monitoring of all incoming and outgoing calls to capture the following information:

- Time and date of call
- Contact type
- Name and position of site personnel making call
- Topic of call (e.g., protocol question, technical assistance, medical information)
- Resolution of call (e.g., completed, next steps, triage)
- Additional comments and questions from the HCP

The database used enables the RCC to categorize calls by contact type, reason for calls, etc. The RCC database enables fast, accurate reporting on the total number of calls

received and made daily, weekly, or monthly or, for example, report on the types of calls or reasons for the calls by contact type.

Calls conducted by the Central Monitoring Associates to the national coordinators facilitate enrollment and retention by minimizing reporter burden in all aspects of the registry.

Additional data quality efforts are focused on minimizing reporter burden through the following approaches:

- Streamlining data collection with simple and concise CRFs that focus on the endpoints of interest as specified in the protocol
- Providing multiple options for submitting data such as phone, fax, or mail and allowing the reporter to select his/her preferred method of communication
- Providing the HCP with information for verification, where applicable, rather than recreating the data at a given contact

Central Monitoring Associates who are intimately involved in the registry handle the query process. The same Central Monitoring Associates who conduct the calls also manage the query resolution process. To assure data quality INC Research has developed a process that proves to be both efficient and effective. The Central Monitoring Associate from the RCC establishes a rapport with the HCPs at first contact and maintains this relationship throughout the data collection and query resolution processes.

A standard query follow-up regimen of four attempts is used at two-week intervals using phone, fax, mail and/or e-mail as appropriate for query resolution. If no further information is obtained on an otherwise evaluable case, the discrepant data fields may be left blank or identified as “Unknown” as appropriate. However, some cases may be flagged as “Lost to Follow-Up” or “Not Valid” if critical data required to evaluate the case is missing or unknown.

5. STUDY LIMITATIONS

The proposed study is based on analysis of prospective cohort data provided by healthcare providers treating patients with BDQ. The following limitations should be considered:

The registry may include bias related to the observational nature of the data and potential lack of data due to loss to follow-up or essential data not collected as routine fields.

These studies are also subject to real-world prescribing practices that may not provide sufficient patient numbers to meet study goals of ascertainment within a reasonable timeframe. Additionally, participation in the registry may influence prescribing of BDQ in routine patient care.

Allocation of treatment is not subject to randomization. Patients will likely be channeled to treatment based on several measured and unmeasured characteristics and based on treatment guidelines. This potentially introduces associations between exposures and outcomes that are confounded.

6. ETHICAL ASPECTS

6.1. Privacy of Personal Data

Confidentiality of patient records will be maintained at all times. All analyses of data will be performed using appropriately de-identified data without access to personal identifying information. All study reports will contain aggregate data only and will not identify individual patients or physicians. Medical record abstraction, if available, will only be performed after receiving a waiver of authorization from the relevant data holder's privacy board and approval from an Institutional Review Board (IRB). At no time during the study will the sponsor receive patient identifying information.

6.2. Informed Consent

Each subject must give written consent according to local requirements after the nature of this research study has been fully explained. The informed consent form (ICF) must be signed before any study-related data is collected. The ICF used must be approved by the reviewing IRB and acceptable to JRD. The ICF should be in accordance with principles that originated in the Declaration of Helsinki, current ICH and GCP guidelines, applicable regulatory requirements, and JRD policy. The collection and processing of personal data from subjects enrolled in this study will be limited to data necessary to fulfill the objectives of the study. Sample data and corresponding relevant clinical data will be made non-identifiable by the removal of personal identifiers.

A subject may withdraw their consent for this research study through the contact information given on the Informed Consent. JRD will not use the collected data upon receipt of such a request. However, data that have already been processed will be retained by JRD to avoid compromising data analysis.

7. ADMINISTRATIVE REQUIREMENTS

7.1. Adverse Event Reporting

This study is based on aggregate analyses, and the sponsor will report aggregate findings as study reports. Due to the prospective design of this study, in instances where an HCP identifies adverse events or serious adverse events, regardless of causality, the events will be captured by staff at the RCC during the registry data collection process, and an AE form will be forwarded to the Sponsor for review and to be entered to the Sponsor's Safety database. The events will be reported as individual case safety reports under timelines as appropriate per company standard operating procedures.

